**5.1.2.6 Secondary Efficacy Endpoint: Progression-free Survival per RECIST v1.1 (PFS)**

PFS is defined as the time from the start of the study treatment until death from any cause or radiographic disease progression assessed per RECIST v1.1 by investigator assessment.

**Table 3 PFS Definition**

PFS		
Situation	Date of Event or Censor	Outcome
No evaluable post-baseline imaging assessments, no death	Date of first dose (Day 1)	Censor
Participant did not receive new anti-cancer therapy (ACT):		
Radiographical progression documented per RECIST v1.1	Date of radiological disease progression	Event
No radiographical progression, but death recorded on eCRF	Date of death	Event
Neither radiographical progression nor death	Date of last disease assessment	Censor
Participant received new anti-cancer therapy (ACT):		
Radiographical progression documented per RECIST v1.1 after new ACT	Date of last radiological assessment before start of new anti-cancer therapy	Censor
Radiographical progression documented per RECIST v1.1 before new ACT	Date of radiological disease progression	Event
No radiographical progression before new ACT but death recorded	Date of last radiological assessment before start of new anti-cancer therapy	Censor
No radiographical disease progression nor death	Date of last radiological assessment before start of new anti-cancer therapy	Censor
Missed >=2 scheduled radiological assessments		
If radiographical progression or death occurs after missing 2 scheduled radiological assessments	Date of last radiological assessment before missing 2 scans	Censor

PFS = Date of Event or Censor – Date of First Dose +1

Missing 2 scheduled imaging assessments:

Missing 2 scheduled imaging assessments is defined as the gap between two imaging assessments as more than 140 days (2.5 times the scheduled imaging assessment interval (2.5 x 56 days)). Imaging assessments after first iUPD will be excluded in PFS derivation.

Note: Participant cannot be censored at “NE”. If NE is the only previous assessment, then PFS will be censored at Day 1.

To apply the cut-off date to PFS is to exclude those tumor assessments after cut-off date and anti-cancer therapy date after cut-off date in the analysis.

**5.1.2.7 Secondary Efficacy Endpoint: Duration of Response per iRECIST (iDOR)**

iDOR is defined as the time from the date of the first response iCR/iPR (whichever is first recorded) to the date of radiographical progression or date of censoring. iDOR will be calculated only for the subgroup of participants with confirmed response iCR/iPR per iRECIST for investigator assessment.

**Table 4 iDOR Definition**

iDOR		
Situation	Date of Event or Censor	Outcome
Participant did not receive new anti-cancer therapy (ACT)		
iCPD	First date where iUPD criteria are met	Event
No iCPD nor death and NOT in one of the following cases : a) the participant stops protocol treatment because they were not judged to be clinically stable, b) no further response assessments are done (because of participant refusal, protocol non-compliance); c) the next timepoint responses are all iUPD, and iCPD never occurs;	Date of last radiological assessment	Censor
No iCPD nor death and is in one of the following cases : a) the participant stops protocol treatment because they were not judged to be clinically stable, b) no further response assessments are done (because of participant refusal, protocol non-compliance); c) the next timepoint responses are all iUPD, and iCPD never occurs;	First date where iUPD criteria are met	Event
Participant received new anti-cancer therapy (ACT)		
No progression before new ACT	Date of last radiological assessment before start of new ACT	Censor
iCPD before new ACT	First date where iUPD criteria are met	Event
iUPD before new ACT and NOT in one of the following cases : a) the participant stops protocol treatment because they were not judged to be clinically stable, b) no further response assessments are done (because of participant refusal, protocol non-compliance); c) the next timepoint responses are all iUPD, and iCPD never occurs;	Date of last radiological assessment before start of new ACT	Censor
iUPD before new ACT and is in one of the following cases : a) the participant stops protocol treatment because they were not judged to be clinically stable, b) no further response assessments are done (because of participant refusal, protocol non-compliance); c) the next timepoint responses are all iUPD, and iCPD never occurs;	First date where iUPD criteria are met	Event
Missed <math>\geq 2</math> scheduled radiological assessments		
If last assessment prior to missing $\geq 2$ scans is iUPD	First date where iUPD criteria are met	Event
If last assessment prior to missing $\geq 2$ scans is not iUPD and no progression after missing $\geq 2$ scans	Date of last radiological assessment	Censor
If radiographical progression occurs after missing 2 scheduled radiological assessments and last assessment prior to missing $\geq 2$ scans is not iUPD	Date of last radiological assessment before missing 2 scans	Censor

iDOR = Date of Event or Censor – Date of First iCR/iPR +1

Missing 2 scheduled imaging assessments:

Missing 2 scheduled imaging assessments is defined as the gap between two imaging assessments as more than 140 days (2.5 times the scheduled imaging assessment interval [2.5 x 56 days]). Imaging assessments after first iUPD will be excluded in DOR derivation.

Note: Participant cannot be censored at “NE”. If NE is the only previous assessment, then DOR/iDOR will be censored at Day 1.

To apply the cut-off date to DOR/iDOR is to exclude those tumor assessments after cut-off date and anti-cancer therapy date after cut-off date in the analysis.

**5.1.2.8 Secondary Efficacy Endpoint: Duration of Response per RECIST v1.1 (DOR)**

DOR is defined as the time from the date of the first response CR/PR (whichever is first recorded) to the date of radiographical progression or date of censoring. DOR will be calculated only for the subgroup of participants with confirmed response CR/PR per RECIST v1.1 for investigator assessment.

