**Table 2 iPFS Definition**

iPFS		
Situation	Date of Event or Censor	Outcome
No evaluable post-baseline imaging assessments, no death	Date of first dose (Day 1)	Censor
Participant did not receive new anti-cancer therapy (ACT):		
iCPD	First date where iUPD criteria are met	Event
No iCPD, but death recorded on eCRF	Date of death	Event
No iCPD nor death and not in one of the following cases : a) if the participant stops protocol treatment because they were not judged to be clinically stable, b) no further response assessments are done (because of participant refusal, protocol non-compliance, or participant death); c) the next timepoint responses are all iUPD, and iCPD never occurs;	Date of last radiological assessment	Censor
No iCPD nor death and is in one of the following cases : a) if the participant stops protocol treatment because they were not judged to be clinically stable, b) no further response assessments are done (because of participant refusal, protocol non-compliance, or participant death); c) the next timepoint responses are all iUPD, and iCPD never occurs;	First date where iUPD criteria are met	Event
Participant received new anti-cancer therapy (ACT):		
No progression before new ACT	Date of last radiological assessment before start of new anti-cancer therapy	Censor
iCPD before new ACT	First date where iUPD criteria are met	Event
iUPD before new ACT and not in one of the following cases: a) if the participant stops protocol treatment because they were not judged to be clinically stable, b) no further response assessments are done (because of participant refusal, protocol non-compliance, or participant death); c) the next timepoint responses are all iUPD, and iCPD never occurs;	Date of last radiological assessment before start of new anti-cancer therapy	Censor
Table continued on next page		

iPFS		
Situation	Date of Event or Censor	Outcome
iUPD before new ACT and is in one of the following cases : a)if the participant stops protocol treatment because they were not judged to be clinically stable, b) no further response assessments are done (because of participant refusal, protocol non-compliance, or participant death); c) the next timepoint responses are all iUPD, and iCPD never occurs;	First date where iUPD criteria are met	Event
Missed <math>\geq 2</math> scheduled radiological assessments		

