**Table 5 DOR Definition**

DOR		
Situation	Date of Event or Censor	Outcome
Participant did not receive new anti-cancer therapy (ACT)		
Radiographical progression documented per RECIST v1.1	Date of radiological PD	Event
No radiographical progression	Date of last radiological assessment	Censor
Participant received new anti-cancer therapy (ACT)		
Radiographical progression documented per RECIST v1.1 after new ACT	Date of last radiological assessment before start of new anti-cancer therapy	Censor
Radiographical progression documented per RECIST v1.1 before new ACT	Date of radiological PD	Event
No radiographical progression	Date of last radiological assessment before start of new anti-cancer therapy	Censor
Missed >=2 scheduled radiological assessments		
If radiographical progression or death occurs after missing 2 scheduled radiological assessments	Date of last radiological assessment before missing 2 scans	Censor

DOR = Date of Event or Censor – Date of First CR/PR +1

Missing 2 scheduled imaging assessments:

Missing 2 scheduled imaging assessments is defined as the gap between two imaging assessments as more than 140 days (2.5 times the scheduled imaging assessment interval [2.5 x 56 days]).

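### Death is never an event for duration of response: DOR censors it at the last scan, and iDOR leaves one class of deaths with no row

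*SAP*

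**What the plan says.** The text definitions of iDOR (SAP 5.1.2.7) and DOR (SAP 5.1.2.8) share the same end: "to the date of radiographical progression or date of censoring". Death is not mentioned in either.

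**Table 5 (DOR).** Without new anti-cancer therapy there are two rows: progression, which is an event, and "No radiographical progression", which is censored at the last scan. Death appears only in the missed-scan row, "If radiographical progression or death occurs after missing 2 scheduled radiological assessments", and that row also censors.

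**Table 4 (iDOR).** Without new therapy, one row covers iCPD. The other two cover participants without iCPD, and both exclude deaths; the first begins "No iCPD nor death and NOT in one of the following cases".

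**Tables 2 and 3 (iPFS, PFS).** Each has a row that makes death an event on its own date: "No iCPD, but death recorded on eCRF" and "No radiographical progression, but death recorded on eCRF".

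**Planned output.** Protocol Section 9.4.2.3 plans Kaplan-Meier estimates for DOR and iDOR by dose level but does not define where either endpoint ends. SAP Sections 6.4.2.7 and 6.4.2.8 plan listings only. SAP Section 1 explains that the plan was cut back because the study stopped early.

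**The concern.** A response cannot continue after death, so a death without documented progression ends it. Censoring such a death is informative. It also makes the duration endpoints disagree with PFS and iPFS for the same person, and the SAP gives no reason for the difference.

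The wording suggests that the death row was lost rather than deliberately left out. Table 4 still excludes deaths from its no-iCPD rows, as though another row dealt with them, but none does. Table 5 still names death in its missed-scan row although death is never an event there.

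Even a listing needs a date and a status for every confirmed responder. As written, two programmers could derive different iDOR records from the same data.

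**Working it through.** The documents give no number of responders, no DOR event count and no share of deaths without progression, so there is no planned figure to reproduce. The check is a reading of SAP Tables 2 to 5 side by side.

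**Step 1. One participant through four tables.** Take a confirmed responder who dies with no PD or iCPD, no new anti-cancer therapy and no missed-scan gap. The SAP sets that gap at more than 2.5 × 56 = 140 days between scans.

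| Endpoint | Row that applies | Date used | Status |
|---|---|---|---|
| PFS (Table 3) | "No radiographical progression, but death recorded on eCRF" | Death | Event |
| iPFS (Table 2) | "No iCPD, but death recorded on eCRF" | Death | Event |
| DOR (Table 5) | "No radiographical progression" | Last scan | Censored |
| iDOR (Table 4) | None | Undefined | Undefined |

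**Step 2. Other deaths.**
- Death after new therapy without earlier progression: all four tables censor at the last scan before that therapy, so there is no conflict.
- Death after two missed scans: Table 5 censors, as does Table 3. Table 4 does not name death in its missed-scan rows, whereas Table 2 does. If the last scan before the gap was not iUPD, such a death reaches a Table 4 censoring row only through the absence of later progression.

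The disagreement with PFS and iPFS is therefore confined to the class in Step 1.

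**Step 3. Effect on a listed DOR value.** Let R be the date of first response, L the last scan and D the death, with D ≥ L.
- As written: L − R + 1, censored.
- With death counted: D − R + 1, event.
- Difference: D − L ≥ 0.

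The listed duration stays equal or becomes longer, and the status changes to event. If the 140-day rule is also taken to run from last scan to death (an assumption; the SAP defines it only between scans), the difference is at most 140 days.

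**Step 4. What a Kaplan-Meier analysis would do.** This is an illustration, not a figure from the documents. Assume exponential times with total hazard λ for progression or death, and let a share f of responses end in death without progression.
- Median with death counted: ln 2 / λ.
- Median with deaths censored at the time of death: ln 2 / ((1 − f)λ).
- Ratio: 1 / (1 − f).

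| Assumed f | Ratio of medians |
|---|---|
| 5% | 1/0.95 = 1.05 |
| 10% | 1/0.90 = 1.11 |
| 20% | 1/0.80 = 1.25 |
| 30% | 1/0.70 = 1.43 |

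**Step 5. Death after an unresolved iUPD.** In Table 4, case b) reads "no further response assessments are done (because of participant refusal, protocol non-compliance" and stops there. In Table 2 the same case reads "no further response assessments are done (because of participant refusal, protocol non-compliance, or participant death" and is dated at the first iUPD. But Table 2 places that case under a row for participants who have not died, while its separate death row gives the death date. The two overlap, so copying Table 2 into Table 4 would not settle which date to use.

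**The case against.** The strongest case against this point has four parts.

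1. **For DOR, text and table agree.** Both stop at radiographic progression or censoring, the missed-scan row that names death also censors, and the protocol sets no other end. On this view it is a choice of definition, not a contradiction. It is true that Table 5 matches its own text. But the choice is not justified, and it gives the participant in Step 1 a different status from PFS.
2. **For iDOR, the omission may be partly deliberate.** Compared with Table 2, Table 4 drops death from case b) and from the missed-scan rows. That is possible, but it does not supply the missing row. An intention to censor would still need a date and a status.
3. **The gap is narrow and little information is lost.** Deaths after new therapy or missed scans are censored in line with PFS, and OS, PFS and iPFS are listed with death as an event. This stands, and it limits the weight of the point.
4. **Nothing reported is biased upwards.** A reader might infer that the trial's reported duration of response would be overstated, or that a responder who dies is credited with response up to death. The documents support neither. DOR stops at the last scan, so the listed value is equal to or shorter than the time to death, and this SAP plans no Kaplan-Meier estimate for DOR or iDOR.

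**Conclusion.** The point holds as a defect of definition. Table 5 gives a confirmed responder who dies without documented progression, new therapy or missed scans a censored DOR at the last scan. Table 4 gives that participant no iDOR record. Tables 2 and 3 count the same death as an event.

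The size is limited to wrong or undefined dates and flags in two listings. The number of participants affected cannot be derived: the documents give no responder count, and Protocol Section 2.3.1.1 reports only 4 treated participants as of 06 May 2022. A percentage of lost events would rest on invented counts.

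Informative censoring would inflate a Kaplan-Meier median only if the analysis in Protocol Section 9.4.2.3 were run. The ratios of 1.05 to 1.43 in Step 4 rest wholly on the assumed 5% to 30% share and on exponential times. They show direction and sensitivity, not an expected effect in this trial.

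**What to change.** - **Text of 5.1.2.7 and 5.1.2.8:** define iDOR and DOR as the time from first response to radiographic progression or death from any cause, whichever is first.
- **Table 5:** add a row for death without radiographic progression, with no new therapy and fewer than two missed scans, as an event at the date of death. Limit the existing row without new therapy, "No radiographical progression", to participants who have not died.
- **Table 4:** add the matching row for death without iCPD, under the same conditions, as an event at the date of death. State which date applies when an unresolved iUPD precedes death, the first iUPD or the death, and use the same rule in Table 2, where the death row and case b) overlap.
- **Missed-scan rows of Table 4:** name death, in line with Table 2.

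If censoring death is intended, the SAP should say so, justify it and still give death without iCPD a row in Table 4.

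The cost is a few lines of SAP text and one derivation rule. For affected participants the listed durations become equal or longer and the status becomes an event.

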**Table 5 DOR Definition**

DOR		
Situation	Date of Event or Censor	Outcome
Participant did not receive new anti-cancer therapy (ACT)		
Radiographical progression documented per RECIST v1.1	Date of radiological PD	Event
No radiographical progression	Date of last radiological assessment	Censor
Participant received new anti-cancer therapy (ACT)		
Radiographical progression documented per RECIST v1.1 after new ACT	Date of last radiological assessment before start of new anti-cancer therapy	Censor
Radiographical progression documented per RECIST v1.1 before new ACT	Date of radiological PD	Event
No radiographical progression	Date of last radiological assessment before start of new anti-cancer therapy	Censor
Missed >=2 scheduled radiological assessments		
If radiographical progression or death occurs after missing 2 scheduled radiological assessments	Date of last radiological assessment before missing 2 scans	Censor

DOR = Date of Event or Censor – Date of First CR/PR +1

Missing 2 scheduled imaging assessments:

Missing 2 scheduled imaging assessments is defined as the gap between two imaging assessments as more than 140 days (2.5 times the scheduled imaging assessment interval [2.5 x 56 days]).

## **5.2 Safety Endpoints**

Safety and tolerability, to determine MTD and RP2D, are the primary endpoints of the study. Safety endpoints are DLTs, adverse events (AEs), laboratory measurements, vital signs, ECGs, physical examinations, and ECOG (Eastern Cooperative Oncology Group) performance status (PS). Safety will be assessed by evaluation of the following variables:

### **5.2.1 Safety Endpoint: Dose-Limiting Toxicity (DLT)**

A DLT is defined as any of the listed events that occur within 28 days starting with the first dose on C1D1 in the dose escalation cohort and that is considered to be related to IP.

Confirmation of DLTs will be made by the DESC. The severity of AEs will be assessed according to National Cancer Institute's Common Terminology Criteria for Adverse Events (NCI-CTCAE). Participants experiencing DLTs, who in the opinion of the investigator are deriving clinical benefit from the study treatment (e.g., marked reduction in tumor burden), may be allowed to continue study treatment with ASP0739 upon resolution of the event to  $\leq$  grade 1 or baseline, upon discussion with the sponsor. Participants experiencing DLTs during the single agent dose escalation portion will not be replaced.

#### **5.2.1.1 Safety Endpoint: ASP0739 Single Agent Dose-Limiting Toxicities (DLTs)**

For participants in the single agent (dose escalation) ASP0739 arm, DLTs are defined in the protocol in Section 4.1.

Participants who are tolerating the IP at a dose level that is being reviewed due to the occurrence of DLTs in another participant will not be automatically precluded from continued dosing during the safety review and will be allowed to continue dosing for as long as tolerated unless directed otherwise as a result of the safety review by the DESC.

Dose escalation within individual participants will not be allowed.

#### **5.2.1.2 Safety Endpoint: ASP0739 Safety Lead-In Dose-Limiting Toxicities (DLTs)**

A DLT is defined as any of the listed events that occur within 28 days starting with the first dose on C1D1 in the safety lead-in cohort and that is considered to be possibly, probably or definitely related to IP. Confirmation of DLTs will be made by the DESC. The severity of AEs will be assessed according to NCI-CTCAE. Participants experiencing DLTs, who in the opinion of the investigator are deriving clinical benefit from the study treatment (e.g., marked reduction in tumor burden), may be allowed to continue study treatment with ASP0739 upon resolution of the event to  $\leq$  grade 1 or baseline, upon discussion with the sponsor.

Participants experiencing DLTs during the combination safety lead-in portion will not be replaced.

#### **5.2.1.3 Safety Endpoint: ASP0739 Dose-Limiting Toxicities (DLTs)**

For participants in the ASP0739, DLTs are defined in the protocol in Section 4.1.

Participants who are tolerating the IP at a dose level that is being reviewed due to the occurrence of DLTs in another participant will not be automatically precluded from

continued dosing during the safety review, and will be allowed to continue dosing for as long as tolerated unless directed otherwise as a result of the safety review by the DESC.

Dose escalation within individual participants will not be allowed.

### **5.2.2 Safety Endpoint: Maximum Tolerated Dose (MTD) and Recommended Phase 2 Dose (RP2D)**

#### Maximum Tolerated Dose

The MTD determination will be based on at least 6 evaluable participants at that dose level based on the BOPIN design. Based on the observed DLT(s) during the DLT observation period, the MTD is the highest dose for which the isotonic estimate of the DLT rate is closest to, but not over, the target DLT rate of 0.30 for monotherapy and combination therapy.

The dose level determined to be the MTD must have data from at least 6 participants.

Determination of MTD will be done for monotherapy.

#### Recommended Phase 2 Dose (RP2D)

The sponsor, in conjunction with the DESC, will determine the RP2D of ASP0739 as a single agent taking into consideration the safety and efficacy data, as well as other available data, such as pharmacokinetics and pharmacodynamics of ASP0739. The RP2D will not exceed the MTD. Additionally, only when determining the RP2D, the DESC may choose a more conservative dosing decision than the maximum tolerated dose (MTD) selected by BOPIN design, based on evaluation of the safety data and other available data.

The dose level determined to be the RP2D must have data from at least 6 participants.

Determination of RP2D will be done for monotherapy.

### **5.2.3 Safety Endpoint: Adverse Events (AEs)**

An AE is any untoward medical occurrence in a participant or clinical study participant, temporally associated with the use of study IP and other study treatments, whether or not considered related to the study IP and other study treatments.

A treatment-emergent adverse event (TEAE) is defined as an AE observed after starting administration of the IP until 30 days after the final administration of IP. An IP-related TEAE is defined as any TEAE with a causal relationship assessed as “yes” by the investigator or with missing assessment of the causal relationship.

If the adverse event occurs on Day 1 and the onset check box is marked “Onset after first dose of study IP” or the onset check box is left blank, then the adverse event will be considered treatment emergent. If the adverse event occurs on Day 1 and the onset check box is marked “Onset before first dose of study IP”, then the adverse event will not be considered treatment emergent. If a participant experiences an event both during the pre-investigational period and during the investigational period, the event will be considered as TEAE only if it has worsened in severity (i.e. it is reported with a new start date). All adverse events

collected that begin within 30 days after taking the last dose of study IP will also be counted as TEAE.

The number and percentage of participants with TEAEs, IP-related TEAEs, serious TEAEs, IP-related serious TEASs, TEAEs leading to withdrawal of treatment and IP-related TEAEs leading to withdrawal of treatment will be summarized by SOC, preferred term and treatment group. The number and percentage of TEAEs by severity will also be summarized. The worst severity will be summarized if the same AE is recorded more than once for a participant.

AE data will be listed.

Immune-related AE (irAE) and infusion related reactions (IRR) will be considered as Adverse Events of Special Interest (AEsi). The list of events classified as AEsi may change during the study due to ongoing pharmacovigilance.

Time to first onset of irAE will follow the following algorithm:

Situation	Date of Event or Censor	Outcome
AE of interest observed	Date of first onset	Event
No AE of interest observed and treatment ongoing	Date of data cutoff	Censor
No AE of interest observed and treatment discontinued	Date of last dose + 30 days	Censor

Time to First Onset = Date of Event or Censor – Date of First Dose +1

